An adverse event is any untoward medical occurrence in a subject who has received an intervention (drug, biologic, or other intervention). The occurrence does not necessarily have to have a causal relationship with the treatment. An AE can therefore be any unfavorable or unintended sign (including an abnormal laboratory finding, for example), symptom, or disease temporally associated with the use of a medicinal product, whether or not considered related to the medicinal product. Adverse event monitoring for the emergency department phase would start at the time of randomization and end at two hours after initial medication administration. Any additional adverse events that occur beyond 120 minutes after initial medication administration will be obtained during the 30 day follow up phone call.

All AEs (including serious AEs) will be noted in the study records and on the case report form with a full description including the nature, date and time of onset, determination of non-serious versus serious, intensity (mild, moderate, severe), duration, causality, and outcome of the event. SAEs will be reported within 24 hours.

Definition of a Serious Adverse Event (SAE)

An SAE is any adverse drug experience occurring at any dose that results in any of the following outcomes:

- death
- a life-threatening event (at risk of death at the time of the event)
- requires inpatient hospitalization or prolongation of existing hospitalization
- a persistent or significant disability/incapacity
- results in a congenital anomaly or birth defect

Important medical events that may not result in death, be life-threatening, or require hospitalization may be considered a serious adverse drug event when, based upon appropriate medical judgment, they may jeopardize the subject and may require medical or surgical intervention to prevent one of the outcomes listed in this definition. The one exception to these criteria is hospitalization for repair and/or pain management associated with the injury. Since this can be expected as part of the standard treatment course for orthopedic injuries, admissions for this reason will not be reported as a serious adverse event. However, all admissions will be tracked and those related to adverse events or for reasons other than injury repair or pain management will be reported as an SAE.

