Serious adverse event monitoring starts at the time of consent and ends at the time of discharge or admission. All SAEs will be followed until resolution, the event is considered to be medically stable, or for 30 days after the subject completes the study, whichever occurs first.

A distinction should be drawn between serious and severe AEs. A severe AE is a major event of its type. A severe AE does not necessarily need to be considered serious. For example, nausea which persists for several hours may be considered severe nausea, but would not be an SAE. On the other hand, a stroke that results in only a limited degree of disability may be considered a mild stroke, but would be an SAE.

Serious Adverse Events (SAEs) Specific to this Study

There has been documentation of a few significant adverse effects associated with the medications included in this study. These effects are exceedingly rare and are anticipated to be even rarer through an intranasal route of drug administration compared with an intravenous route and with sub-dissociative dosing of ketamine as compared with dissociative dosing.

Ketamine: cardiac arrhythmia, hypertensive emergency, prolonged emergence reaction, anaphylaxis, laryngospasm, apnea

Fentanyl: cardiac arrhythmia, cardiopulmonary arrest, chest wall rigidity, hypertensive emergency, hypotension, pulmonary embolism, anaphylaxis, apnea, bronchospasm, laryngospasm

In the exceedingly rare instance that one of these serious adverse effects was to occur, the patient would be treated for that particular emergency in a manner that is standard of care at CCHMC were the emergency to occur in any other setting.

Relationship of SAE to study drug or other intervention

The relationship of each SAE to the study intervention should be characterized using one of the following terms in accordance with CCHMC IRB Guidelines: definitely, probably, possibly, or unrelated.

Monitoring Plan

The medical monitor is the person responsible for the safety monitoring in this protocol and he will monitor all clinically significant adverse events (AEs) and provide consultation for any AEs that the investigators question the classification, severity or relatedness originally documented at the time of the ED visit. The medical monitor will be [name]. He is a member of the Division of Emergency Medicine, who will not be involved with enrollment.

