AEs will be reported to the IRB as detailed below. Adverse events will be recorded on the study data form by the study team. Any serious adverse events (SAEs) will be reported to the investigator or designee immediately. Study forms and charts will be reviewed by the study coordinator and principal investigator for AEs after the ED visit. All identified AEs will be recorded. The investigator will determine the grade and attribution. If unblinding is required, the investigator will notify the IRB. The protocol and consent will be reviewed by the investigator to determine if any changes are required. SAE's that are related to the study and unexpected will be reported to the IRB and FDA. Any serious adverse events and/or adverse events that occur during the study will be followed to resolution.

For the purpose of this study, toxicity is defined using the Common Terminology Criteria for Adverse Events (CTCAE) v4.0 as defined by the National Cancer Institute (<http://ctep.cancer.gov/reporting/ctc.html>).

Grade level 4 or greater toxicity which are unexpected and related to the study will be reported to the IRB within 48 hours. Examples pertinent to this protocol include: life threatening respiratory compromise resulting in intubation, anaphylaxis, hypotension, hypertensive crisis, life-threatening cardiac arrhythmias requiring urgent intervention, nausea and emesis with life-threatening consequences, and change in mental status including states harmful to the subject.

Subjects will be withdrawn from study drug exposure if any of the following events occur during the patient's stay in the ED:

- The subject has a SAE possibly or definitely related to the study drug
- The subject experiences a level 4 toxicity as defined by CTCAE
- The subject experiences one or more level 3 toxicities as defined by CTCAE
- The subject has an adverse event experience that would, in the investigator's judgment, make continued participation in the study not in the subject's best medical interest.

The trial will stop enrollment for the following events:

- A SAE rate related to the study intervention of greater than or equal to 2 in 10 subjects is detected
- Subjects experiencing grade 3 toxicities occur more frequently than 3 in 10 subjects.

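### The toxicity rule for stopping enrolment counts grade 3 only, so swapping one grade 3 event for a grade 4 event can keep enrolment open

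*Combined protocol and SAP*

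**What the plan says.** The Monitoring Plan in section XIII lists two events that stop enrolment. The first concerns SAEs and reads "A SAE rate related to the study intervention of greater than or equal to 2 in 10 subjects is detected". The second is the toxicity rule, which is met when "Subjects experiencing grade 3 toxicities occur more frequently than 3 in 10 subjects".

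Neither rule mentions grade 4 or 5, and nothing in the document adds the two counts together. The SAE rule requires relatedness; the toxicity rule does not.

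Elsewhere in the same section the grades are kept apart. For reporting, the text says "Grade level 4 or greater toxicity which are unexpected and related to the study will be reported to the IRB within 48 hours". The list of reasons for withdrawing a subject has one entry reading "The subject experiences a level 4 toxicity as defined by CTCAE" and another reading "The subject experiences one or more level 3 toxicities as defined by CTCAE".

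The SAE definition in section XIII includes life-threatening events, so a grade 4 event of that kind can enter the SAE rule. Relatedness of an SAE is recorded as "definitely, probably, possibly, or unrelated". The withdrawal list uses a shorter form: "The subject has a SAE possibly or definitely related to the study drug".

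**The concern.** A pair of stopping rules should not let enrolment continue on a safety profile that is worse than one that would stop it. Here the milder count has its own threshold, the more severe count has a different one, and moving a subject from the first to the second lowers the first count. If the second count is still below its threshold, neither rule is met.

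The relatedness condition adds a second asymmetry. An unrelated grade 3 event counts towards stopping; an unrelated grade 4 event counts nowhere. Section XIII has the investigator determine grade and attribution, so an attribution decision can take a grade 4 event out of both rules.

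At stake is whether the written thresholds respond in the right direction in a trial of children aged 8 to 17.

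**Working it through.** The plan gives thresholds only, with no derived figure to reproduce. The check is a direct count.

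**Inputs** (section XIII, Monitoring Plan). Let n be the number of subjects, a the number with grade 3 toxicity, and s the number with a related SAE.

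- Toxicity rule: stop if a/n > 3/10.
- SAE rule: stop if s/n ≥ 2/10.

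**Assumptions.** Each subject is counted once, at the highest grade. The grade 3 events are not themselves related SAEs. Every grade 4 event qualifies as an SAE, which fits the life-threatening examples in section XIII.

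**Ten subjects.** Start from the smallest grade 3 count that stops enrolment, which is 4, and replace grade 3 subjects with grade 4 subjects one at a time.

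| Grade 3 | Grade 4 | Toxicity rule | SAE rule, grade 4 related | Result if related | Result if unrelated |
|---|---|---|---|---|---|
| 4 | 0 | 4/10 > 3/10, met | 0/10, not met | stop | stop |
| 3 | 1 | 3/10, not above 3/10 | 1/10 < 2/10, not met | **open** | **open** |
| 2 | 2 | 2/10, not met | 2/10, met | stop | **open** |
| 1 | 3 | 1/10, not met | 3/10, met | stop | **open** |
| 0 | 4 | 0/10, not met | 4/10, met | stop | **open** |

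With related events, exactly one replacement escapes. With unrelated events, every replacement escapes.

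**Twenty subjects**, taking the rate over all subjects so far. Seven grade 3 subjects stop enrolment (7/20 = 35%). Six grade 3 plus one related grade 4 do not (6/20 = 30%, not above 30%; 1/20 = 5%). Nor do four plus three (4/20 = 20%; 3/20 = 15%). Three plus four do (4/20 = 20% meets the SAE rule). So the reversal is not peculiar to n = 10.

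**With the toxicity rule counting grade 3 or greater**, the profile of three plus one in ten gives (3 + 1)/10 = 4/10 > 3/10, and enrolment stops, as it does for four grade 3 subjects. The same holds for unrelated grade 4 events, because the toxicity rule has no relatedness condition. Any profile that stops under the present text still stops, since the toxicity count can only rise.

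**The case against.** The strongest reply is that serious related events already face the stricter rule: 2 in 10 is enough, against more than 3 in 10 for grade 3. Two related grade 4 subjects in ten stop the trial; two grade 3 subjects do not. This stands. A reader might infer that the rules become generally less likely to trigger as events get worse. For related events they do not; the order reverses only for certain mixtures.

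A reader might also infer that, with no interim analysis planned, these two rules are the only protection. The documents do not support that. The Interim Analysis paragraph in section VIII promises continuing review of adverse events, SAEs and toxicities. Section XIII names a medical monitor and sets prompt reporting of SAEs and of related, unexpected grade 4 or higher toxicity. None of these carries a numerical threshold, so they limit the consequence of the gap but do not close it.

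A third inference is a large worst case. Over the 90 planned subjects, 27 with grade 3 (27/90 = 30.0%) and 17 with related grade 4 or 5 (17/90 = 18.9%) would meet neither rule, giving 44/90 = 48.9%. That is a constructed bound, not the size of the problem. It needs 17 related serious events in a trial whose Safety Analysis paragraph anticipates none. It also needs no grade 4 subject to have had a grade 3 toxicity as well, and a cumulative denominator that the plan does not specify.

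It can also be said that grade 3 may be loose wording for a floor, since the withdrawal list names level 4 without adding that higher grades count. That is possible, but the reporting clause does spell out a floor, so the enrolment rule cannot safely be read as having one. Finally, leaving unrelated events out of a drug-related SAE rule is an ordinary choice. That is fair for the SAE rule alone; the oddity is that the toxicity rule counts unrelated grade 3 events and not unrelated grade 4 events.

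**Conclusion.** The concern holds in a limited form. As written, the two enrolment rules can rank profiles the wrong way round: in ten subjects, four grade 3 stop enrolment, and three grade 3 plus one related grade 4 do not. For related events at n = 10 the gap is a single replacement. For grade 4 events judged unrelated it extends to all four.

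The related-event result rests on counting each subject once at the highest grade and on the grade 3 events not being related SAEs. If a grade 4 subject also counted for an earlier grade 3 toxicity, or if one of the remaining grade 3 events were a related SAE, the three-plus-one profile would stop. The plan does not settle either point.

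The wording of the withdrawal list is a separate, minor matter. A reader might infer from its omission of *probably* that probably related SAEs drop out of the enrolment rule. They do not: that rule asks only for relatedness to the intervention, and on the four-term scale the only category outside it is *unrelated*.

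The amendment is worth making because a stated rule gives a wrong result, although the events needed to reach it are expected to be rare.

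**What to change.** In the Monitoring Plan of section XIII, have the second enrolment rule count subjects with grade 3 **or greater** toxicity, each subject once. Leave both thresholds and the SAE rule as they are.

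Separately, the sponsor should reconcile the relatedness terms in the withdrawal list with the four-term scale earlier in section XIII.

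The cost is a few words in an amendment. The downside is that enrolment may pause slightly sooner, but only if grade 4 or 5 events occur. Section XIII already describes the review and reopening that would follow a pause.

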Afridi, 2013	18	18-57	Inpatient and Outpatient, London	Randomized double blind parallel controlled trial: Ketamine vs Midazolam	Ketamine 25 mg Midazolam 2 mg	IN	Ketamine reduced the severity but not the duration of aura, whereas midazolam as no effect

Riediger, 2015	22	≥18 years	Postoperative Switzerland	Randomized double blind noninferiority trial: S-Ketamine+Midazolam Vs Morphine	S-ketamine 6 mg alternating with Midazolam 0.75 mg (lockout interval of 20 min between meds) Morphine 2 mg (lockout interval of 12 min)	IN	Similar NRS scores in morphine and S-ketamine groups as 1, 2, 4, 24, 48 and 72 hours after surgery. No difference in bolus demands and deliveries of medications.
Messenger, 2008	63	14-65 years	Emergency Department, Canada	Randomized double blind controlled trial: ketamine vs fentanyl (followed by propofol)	Ketamine 0.3 mg/kg Fentanyl 1.5 mcg/kg	IV	Ketamine and fentanyl have similar efficacy. Sub-dissociative ketamine is safer than fentanyl for ED procedural sedation and analgesia with propofol.
Galinski, 2007	65	18-70 years	Emergency Department, France	Multicenter, randomized double blind trial: Ketamine + morphine vs Normal saline + morphine	Ketamine 0.2 mg/kg Morphine 0.1 mg/kg	IV	Morphine consumption significantly lower in ketamine group than placebo (0.149 mg/kg vs 0.202 mg/kg). No significant difference in VAS score at 30 minutes
Gurnani, 1996	40	Adult	Emergency Department, India	Randomized double blind pilot trial: Ketamine dose followed by infusion vs Morphine dose followed by q4 hour dosing	Ketamine 0.25 mg/kg initial dose, infusion at 0.1 mg/kg/hr Morphine 0.1 mg/kg initial dose, 0.1 mg/kg q4	IV	VAS scores significantly lower in ketamine group. Patients in ketamine group significantly less drowsy. No ketamine patients required supplemental analgesia vs 90% of morphine patients required supplemental analgesia
Motov, 2015	90	18-55 years	Emergency Department, USA	Randomized double blind trial: Ketamine vs Morphine	Ketamine 0.3 mg/kg Morphine 0.1 mg/kg	IV	Ketamine is as effective as morphine for analgesia at 15 and 30 minutes (8.6 vs 8.5 at baseline, 3.2 vs 4.2 at 30 minutes)
Miller, 2015	45	18-59 years	Emergency Department, USA	Randomized controlled double blind superiority trial: Ketamine vs Morphine	Ketamine 0.3 mg/kg Morphine 0.1 mg/kg	IV	Ketamine did not produce a greater reduction in NRS scores compared with morphine. Time to achieve maximum reduction in NRS was 5

							min for ketamine and 100 min for morphine
Tran, 2014	308	>30 months	Prehospital trauma, Vietnam	Prospective, cluster randomized study: Ketamine vs Morphine	Ketamine 0.2-0.3 mg/kg Morphine 10 mg (adults) 5 mg (children)	IV IM	Ketamine provided an analgesic effect equal to that of morphine, no significant differences between the two groups.
Beaudoin, 2014	60	18-65 years	Emergency Department, USA	Randomized controlled double blind trial: Morphine/NS Vs Morphine/Ketamine 1 Vs Morphine/Ketamine 2	Morphine 0.5 mg/kg Ketamine 1 0.15 mg/kg Ketamine 2 0.3 mg/kg	IV	SPIDs (summed pain intensity difference) were higher for the ketamine groups. Patients in morphine group required rescue analgesia sooner than the ketamine groups. Patients with the higher ketamine dose sustained analgesic effect longer.
Lester, 2010	35	21-57 years	Emergency Department, USA	Retrospective chart review: low dose ketamine as adjunct to opioids	0.1-0.6 mg/kg (5-35 mg)	IV (30) IM (5)	Improvement in pain in 54% of cases
Johansson, 2009	27	Adults	Prehospital trauma, Sweden	Prospective cohort study: Morphine vs Morphine+Ketamine	Morphine 0.2 mg/kg Morphine (0.1 mg/kg) + Ketamine (0.2 mg/kg)	IV	Ketamine/morphine group had significant lower NRS scores than morphine alone (5.4±1.9 vs 3.1±1.4)
Ahern, 2013	30	23-62 years	Emergency Department, USA	Prospective observational study: Hydromorphone + Ketamine	Hydromorphone (0.5 mg) Ketamine (15 mg)	IV	Mean reduction in NRS score at 5 min was 6 and at 15 min was 5. SPID at 30 min was 25 and at 60 min was 41. (This protocol provided profound, rapid pain relief)
Jennings, 2012	135	≥18 years	Prehospital trauma, Australia	Prospective, randomized controlled multicenter study: Morphine alone vs Morphine+Ketamine	Morphine 5 mg every 5 min until pain free Morphine 5 mg + Ketamine 10 or 20 mg then 10 mg every 3 min until pain free	IV	Morphine plus ketamine provides analgesia superior to that of morphine alone. (mean NRS reduction of 5.6 vs 3.2). Ketamine had a quicker reduction of pain intensity.

APPENDIX B: Clinical Studies of Sub-dissociative (Intranasal and Intravenous) and Dissociative (Intranasal) Dose Ketamine in Children

[figure not shown]
Study	N	Ages	Setting	Design	Doses	Route	Outcome
Graudins, 2015 Ketamine for analgesia (sub-dissociative low dose)	73	3-13 years	Emergency Department, Australia	Double blind, randomized controlled trial: Fentanyl vs Ketamine	Fentanyl 1.5 mcg/kg Ketamine 1 mg/kg	IN	Median reduction in VAS score at 30 minutes for ketamine was 45 mm and for fentanyl was 40 mm (no significant difference between groups), which was maintained to 60 minutes in both groups.
Yeaman, 2013 Ketamine for analgesia (sub-dissociative low dose)	28	3-13 years	Emergency Department, Australia	Observational study: Ketamine	Ketamine 0.8-1.48 mg/kg	IN	IN ketamine provided adequate analgesia by 30 minutes. Median VAS decreased from 74.5 mm to 30 mm.
Johansson, 2013 Ketamine for analgesia (sub-dissociative low dose)	9	7-36 years	Prehospital trauma, Sweden	Case series: (S)-Ketamine	Ketamine 0.45 mg/kg-1.25 mg/kg	IN	IN S-ketamine provided adequate analgesia. Median pain score decreased from 10 to 3 (on a 10 point scale).
Nielsen, 2013 Ketamine for analgesia (sub-dissociative low dose)	50	0.8-17 years	Inpatient, Denmark	Prospective nonrandomized trial: Sufentanil + Ketamine	Sufentanil 0.5 mcg.kg PLUS Ketamine 0.5 mg/kg	IN	Provided rapid analgesia in 78% of patients (decreased pain score to ≤5 on 10 pt scale).
Tsze, 2012 Ketamine for sedation (dissociative dosing)	12	1-7 years	Emergency Department, USA	Randomized, prospective double blind trial: Ketamine (3 doses)	Ketamine #1 3 mg/kg Ketamine #2 6 mg/kg Ketamine #3 9 mg/kg	IN	Significantly higher proportion of successful sedations with 9 mg/kg dose than the other two doses.
Reid, 2011 Ketamine for analgesia (sub-dissociative low dose)	1	9 years	Prehospital, Australia	Case Report: Ketamine	Ketamine 0.5 mg/kg	IN	Provided rapid resolution of pain and effective anxiolysis
Roelofse, 2004 Ketamine for sedation	50	5-7 years	Operating room (Dental), New Zealand	Randomized double blind trial: Sufentanil/Midazolam Vs Ketamine/Midazolam	Sufentanil 20 mcg + Midazolam 0.3 mg/kg	IN	No significant difference in sedation and anxiety levels pre-operatively or in

(dissociative dosing)					Ketamine 5 mg/kg + Midazolam 0.3 mg/kg		postoperative recovery between the 2 groups. Sufentanil group experienced less pain but not statistically significant (P > 0.05).
Bahetwar, 2011 Ketamine for sedation (dissociative dosing)	45	2-6 years	Outpatient Dental Clinic, India	Triple blind randomized trial: Midazolam vs Ketamine vs Midazolam+Ketamine	Midazolam 0.3 mg/kg Ketamine 6 mg/kg Midazolam 0.2 mg/kg plus Ketamine 4 mg/kg	IN	Ketamine alone had the fastest onset of sedation. Sedation success rate with ketamine was 89%, midazolam was 69% and combination group was 84%.
Khatavkar, 2014 Ketamine for sedation (dissociative dosing)	60	1-12 years	Pre-operative, India	Randomized single blind trial: Midazolam vs Midazolam+Ketamine	Midazolam 0.2 mg/kg Midazolam 0.15 mg/kg + Ketamine 1 mg/kg	IN	Sedation score, anxiolysis, reaction to IV insertion, face mask acceptance and emotional reaction were significantly better in Midazolam+Ketamine group
Gyanesh, 2013 Ketamine for sedation (dissociative dosing)	150	1-10 years	Radiology (MRI), India	Randomized double blind trial: Dexmedetomidine vs Ketamine vs Normal saline	Dexmedetomidine 1 mcg/kg Ketamine 5 mg/kg Normal saline	IN	Dexmedetomidine and ketamine were equally effective as premedication. In 90.4% of DXM patients and 82.7% of ketamine patients, anesthesiologists were satisfied with conditions for IV insertion. Total dose of propofol used was less in DXM and ketamine groups.
Buonsenso, 2014 Ketamine for sedation (dissociative dosing)	36	< 14 years	Inpatient, Italy	Randomized double blind placebo controlled trial: Midazolam+Ketamine Vs Normal saline	Midazolam 0.5 mg/kg + Ketamine 2 mg/kg	IN	Significantly better MOPS (Modified Objective Pain Score) reduction in treatment group. Mean MOPS in treatment group was 3.5 vs mean MOPS in placebo group was 7.2
Kennedy, 1998 Ketamine for sedation	260	5-15 years	Emergency Department, USA	Randomized nonblinded trial: Fentanyl+midazolam vs Ketamine+midazolam	Midazolam 0.5 mg/kg Fentanyl 0.5 mcg/kg Ketamine	IV	Patients receiving ketamine had significant reduction in mean OSBD-R scores compared to those

[figure not shown]
(dissociative dosing)					0.5 mg/kg		receiving fentanyl during fracture reduction
Elhakim, 2003 Ketamine for analgesia (sub-dissociative low dose)	50	5-12 years	Preoperative, Egypt	Randomized double blind placebo controlled trial: Ketamine + diclofenac + fentanyl Vs Placebo + diclofenac + fentanyl	Ketamine 0.1 mg/kg Normal saline (same volume) Diclofenac 2 mg/kg Fentanyl 1 mcg/kg	IM	Ketamine group had significantly lower pain scores at rest and on swallowing postoperatively. Ketamine group required less postoperative analgesia.
Finkel, 2007 Ketamine for analgesia (sub-dissociative low dose)	11	3-17 years	Inpatient, USA	Retrospective review: Ketamine infusion in addition to opioid analgesia	Ketamine 0.1-1 mg/kg/hr	IV	73% of patients experienced significant decrease in opioid requirements after ketamine initiated
White, 2011 Ketamine for analgesia (sub-dissociative low dose)	100	3-14 years	Inpatient, United Kingdom	Retrospective review: Morphine PCA Vs Morphine+Ketamine PCA	Morphine PCA 1 mg/kg made up to 50 mL with saline Morphine 1 mg/kg PLUS Ketamine 1 mg/kg PCA made up to 50 mL with saline (bolus 20-40 mcg/kg, infusion 0-40 mcg/kg/hr, max 4h dose of 400 mcg/kg)	IV	Addition of ketamine to the morphine PCA is associated with reduced morphine consumption and improved pain scores.
Taylor, 2014 Ketamine for analgesia (sub-dissociative low dose)	14	1 month-23 years	Inpatient and Outpatient, USA	Retrospective case review: Ketamine PCA in addition to prolonged opioid use	Ketamine 0.014-0.308 mg/kg/hr with demand dose of 0.03/0.5 mg/kg every 10-60 min	IV	All patients with opioid refractory neuropathic pain had improved pain with the addition of ketamine to pain regimen
White, 2006 Ketamine for analgesia (sub-dissociative low dose)	3	12 years	Inpatient, United Kingdom	Case series of patients with toxic megacolon: Ketamine PCA	Ketamine PCA 2 mg/kg made up to 50 mL with 5% dextrose (infusion 0-40 mcg/kg/hr, bolus 20-40 mcg/kg, lockout period 10-30 min)	IV	Improved pain scores in all patients. Safe and effective use of ketamine infusion
White, 2007	1	9 years	Inpatient, Canada	Case report:	Morphine 40 mcg/kg/hr	IV	Long term ketamine infusion (37 days)

Ketamine for analgesia (sub-dissociative low dose)				Ketamine infusion in addition to Morphine infusion	Ketamine 80-200 mcg/kg/hr		provided safe and effective analgesia
Dal, 2007 Ketamine for analgesia (sub-dissociative low dose)	90	2-12 years	Perioperative, Turkey	Randomized placebo controlled trial: Saline vs IV Ketamine bolus vs Peritonsillar ketamine infiltration	Saline 2 mL Ketamine bolus 0.5 mg/kg Ketamine infiltration 0.5 mg/kg	IV	Ketamine groups had significant lower observational pain scores in hospital and at home than saline group. No significant difference in pain score between ketamine groups. Saline group had significantly shorter time to first rescue analgesia.
Bredmose, 2009 Ketamine for analgesia and sedation	164	< 16 years	Prehospital trauma, United Kingdom	Retrospective database review: Ketamine use (68% of these patients also received Midazolam)	Ketamine 0.1-5.8 mg/kg (mean=1.0 mg/kg) Midazolam 0.1-0.5 mg/kg (mean=0.1 mg/kg)	IV/IM	Ketamine provided adequate analgesia and appropriate sedation without major side effects
Zempsy, 2010 Ketamine for analgesia (sub-dissociative low dose)	5	12-18 years	Inpatient, USA	Case series of sickle cell disease patients: Ketamine infusion	Ketamine 0.1-0.2 mg/kg/hr	IV	2 of 5 patients achieved adequate pain control. 1 patient used significantly less opioids.

